10.7 Interim analysis

Scheduled interim analysis will occur for the primary endpoint of clinical benefit rate only as required by the Bayesian Hierarchical design. The first interim analysis will be performed after the first 30 patients have been dosed for at least 16 weeks or discontinued, then every 13 weeks thereafter. Interim analyses may be performed more frequently dependent on enrollment rate to avoid over-enrollment in any of the disease cohorts. At each interim analysis, the groups will be evaluated for early futility and early success by comparing posterior quantities for the response rate to pre-specified early stopping criteria.

There is no plan for a formal interim analysis of safety or other secondary endpoints for this study. However, for publication or other purposes, interim data review of clean data will be performed as necessary. At these interim reviews, patient demographics/baseline characteristics, the primary and secondary endpoints as applicable and all important safety endpoints will be summarized. No formal report will be issued for these interim data reviews.

10.8 Sample size calculation

The sample size was chosen by the usual criteria of obtaining adequate power for the alternative hypothesis of interest as shown in [Section 14.4.4.1](#) of [Appendix R](#). This hypothesis corresponds to a generally effective treatment across groups and incorporates variation in treatment effects to reflect the realistic expectation that treatment effects may differ by group. In this setting, analytical power calculations are not possible, but the design was simulated to obtain the power of the study as shown in the appendix. The sample sizes shown (minimum of 10 for futility stopping, minimum of 15 for early success and maximum of 30 as a group cap) achieve adequate power for the alternative hypothesis. The simulations included the expected

variable accrual by simulating a Poisson process with expected accrual also shown in the [Appendix R](#).

11 Ethical considerations and administrative procedures

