14.1.1.1 Primary analysis

We let $Y_{i\cdot}$ be the response indicator for the i th subject, and let R_g be the assumed probability of response within a control population and $\pi_g = \Pr(Y_{i\cdot} = 1 | g_i = g)$ be the underlying probability of response for group g within the trial. We transform to the logit scale for modeling purposes. Let θ_g be the mean log odds treatment effect, i.e.:

$$\theta_g = \log\left(\frac{\pi_g}{1 - \pi_g}\right) - \log\left(\frac{R_g}{1 - R_g}\right).$$

Thus, θ_g is the group specific logistic regression coefficient for group g . The primary analysis is a set of group specific tests that $\theta_g > 0$, meaning that the experimental treatment is better than the assumed control rate for that group. Thus, we wish to test the set of hypotheses

$$H_0: \theta_g \leq 0$$

$$H_1: \theta_g > 0$$

We proceed in a Bayesian fashion, assigning a prior distribution (discussed below) and computing the posterior probability of H_1 within each group g . If, at the final analysis,

$$\Pr(\theta_g > 0 | \text{data}) > 0.80$$

Then group g will be declared a success (thus, the final analysis produces a separate decision for each group). The trial also allows for early stopping of groups, described below.

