14.4.4.1 Assumptions

Accrual – Two scenarios for the assumed two-year expected accrual are investigated: 1) 10 subjects per group and 2) 5 subjects per group. Note that these are averages, the actual number

of available patients is simulated as a Poisson distribution with the specified mean. Also note that the group cap of 30 applies, and thus if the number of available patients in a group exceeds 30, only the first 30 available patients in that group will be enrolled in the study.

Dropouts – We assume no dropouts for the purpose of this simulation.

Control Rates – [Table 14-1](#) shows the assumed control clinical benefit rates for each group.

Table 14-1 Assumed control CBR values used in the simulations

Tumor Type	Assumed Control Rate (Rg)
Lung LSCL	0.45
Bladder	0.47
Breast	0.50
Colorectal	0.38
GIST	0.50
HNSCC	0.45
Ovarian	0.47
Sarcoma	0.40

We consider four possible scenarios, or possible “truths” in the simulation. These consisted of a null scenario (where the treatment has no effect for any group), an alternative scenario (where the treatment is effective in all groups), a scenario where the treatment was effective in two of the groups, and a scenario where the treatment was effective in half of the groups.

Treatment Rates - The treatment rates for each scenario are shown in the table below. Values identical to the control are shown in red, while values greater than the assumed control rate are shown in green.

	Null	Alternative	Two	Half
Lung LSCL	0.45	0.71	0.45	0.45
Bladder	0.47	0.73	0.47	0.47
Breast	0.50	0.75	0.50	0.50
Colorectal	0.38	0.65	0.38	0.38
GIST	0.50	0.75	0.50	0.75
HNSCC	0.45	0.71	0.45	0.71
Ovarian	0.47	0.73	0.73	0.73
Sarcoma	0.40	0.67	0.67	0.67

Simulation Details – For each scenario we simulated 1000 trials. For each interim within each trial, we ran 50,000 MCMC iterations after a 1,000 MCMC iteration burnin.

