There is no plan for a formal interim analysis of safety or other secondary endpoints for this study. However, for publication or other purposes, interim data review of clean data will be performed as necessary. At these interim reviews, patient demographics/baseline characteristics, the primary and secondary endpoints as applicable, and all important safety endpoints will be summarized. No formal report will be issued for these interim data reviews.

9 Determination of sample size

The sample size was chosen by the usual criteria of obtaining adequate power for the alternative hypothesis of interest as shown in the protocol Tables 4.2 of Appendix R (same as Table 2 as shown below in Section 10.4.2). This hypothesis corresponds to a generally effective treatment across groups and incorporates variation in treatment effects to reflect the realistic expectation that treatment effects may differ by group. In this setting, analytical

power calculations are not possible, but the design was simulated to obtain the power of the study as shown in Section 10 below. The sample size shown (minimum of 10 for futility stopping, minimum of 15 for early success and maximum of 30 as group cap) achieve adequate power for the alternative hypothesis. The simulations included the expected variable accrual by simulating a Poisson process with expected accrual also shown in the protocol Appendix R (same as Section 10 below).

Given the exploratory nature of the study design, there is no power consideration for secondary objectives.

10 Bayesian Adaptive Design

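### Protocol 10.8 and SAP 9 say the powered alternative allows effects to vary by group, but the simulated alternative gives every cohort the same odds ratio of about 3

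*Protocol*

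**What the plan says.** Protocol Section 10.8 opens: "The sample size was chosen by the usual criteria of obtaining adequate power for the alternative hypothesis of interest as shown in"; the reference given there is to Appendix R, Section 14.4.4.1. It describes that hypothesis as a treatment that works generally across groups and one that "incorporates variation in treatment effects to reflect the realistic expectation that treatment effects may differ by group". SAP Section 9 repeats the description: "This hypothesis corresponds to a generally effective treatment across groups and incorporates variation in treatment effects". It points to the power table that the SAP reproduces as Table 2.

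Section 14.4.4.1 lists four simulated truths: no effect anywhere (Null), "an alternative scenario (where the treatment is effective in all groups" (Alternative), effect in two groups (Two), and effect in half of the groups (Half). The rate table gives, in the order Null, Alternative, Two, Half, rows such as "Lung LSCL 0.45 0.71 0.45 0.45", "Bladder 0.47 0.73 0.47 0.47" and "Breast 0.50 0.75 0.50 0.50". The SAP table in Section 10.4.1 has the same values.

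Appendix R Section 14.1.1.1 fixes the scale on which effects are measured. The parameter for each group is the logit of its response rate minus the logit of its assumed control rate, which it takes to "be the mean log odds treatment effect". The borrowing prior is placed on this parameter.

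**The concern.** The design gains power by borrowing across cohorts, and it borrows more when their effects look alike. How much effects vary in the powered scenario therefore bears directly on what the quoted power means. A reader of Section 10.8 would take power above 0.90 at 10 per cohort as already allowing for unequal effects. If the scenario has no such variation, the figure answers a narrower question: power when every cohort has the same, fairly large, effect.

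**Working it through.** **Inputs.** Control rates R and Alternative rates p come from Protocol Section 14.4.4.1, and power from Table 14-2 (SAP Table 2). The effect scale is the log odds ratio of Section 14.1.1.1.

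**Step 1: odds ratios in the Alternative column.** OR = [p/(1−p)] / [R/(1−R)]. The last column applies an odds ratio of exactly 3 to R, that is 3R/(1+2R).

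| Cohort | R | p | OR | p − R | 3R/(1+2R) |
|---|---|---|---|---|---|
| Lung | 0.45 | 0.71 | 2.99 | 0.26 | 0.7105 |
| Bladder | 0.47 | 0.73 | 3.05 | 0.26 | 0.7268 |
| Breast | 0.50 | 0.75 | 3.00 | 0.25 | 0.7500 |
| Colorectal | 0.38 | 0.65 | 3.03 | 0.27 | 0.6477 |
| GIST | 0.50 | 0.75 | 3.00 | 0.25 | 0.7500 |
| HNSCC | 0.45 | 0.71 | 2.99 | 0.26 | 0.7105 |
| Ovarian | 0.47 | 0.73 | 3.05 | 0.26 | 0.7268 |
| Sarcoma | 0.40 | 0.67 | 3.05 | 0.27 | 0.6667 |

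Every entry of the last column rounds to the tabulated p. The log odds ratios run from 1.096 to 1.115 (SD 0.009), against log 3 = 1.099. The column is one common odds ratio of 3, rounded to two decimals.

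**Step 2: the plan's own power for a cohort with odds ratio 3.** These are means over the effective cohorts in Table 14-2.

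| Scenario | 10 per cohort | 5 per cohort |
|---|---|---|
| Alternative (8 cohorts) | 0.920 | 0.812 |
| Half (GIST, HNSCC, ovarian, sarcoma) | (0.826+0.834+0.829+0.852)/4 = 0.835 | (0.688+0.657+0.652+0.667)/4 = 0.666 |
| Two (ovarian, sarcoma) | (0.786+0.758)/2 = 0.772 | (0.587+0.579)/2 = 0.583 |

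An effective cohort's own effect is the same in all three rows, so the differences reflect what the other cohorts are doing. From Alternative to Half and Two, the loss is 0.085 and 0.148 at 10 per cohort, and 0.146 and 0.229 at 5.

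**Step 3: reproducing the tabulated power.** The Appendix R design was re-simulated with 3,000 trials. The posterior was integrated numerically over all partitions of the eight groups. Mean power under Alternative was 0.927 against the plan's 0.920 at 10 per cohort, and 0.804 against 0.812 at 5. Thirteen of the 16 single cells agree within 2 points; the other three miss by 2.1–2.4. Agreement requires three choices: the final cut of 0.80 in Appendix R, the N(0, 1.82) prior read as SD 1.82, and, at 5 per cohort, keeping cohorts with fewer than 3 patients. Removing borrowing gives about 0.79 and 0.61.

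**Step 4: illustration with graded effects.** The documents give no spread, so these are assumptions: log odds ratios normal around log 3, final cut 0.80, 1,200 trials each.

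| SD of log OR | 10 per cohort | 5 per cohort |
|---|---|---|
| 0 (common OR 3) | 0.930 | 0.803 |
| 0.25 | 0.905 | 0.795 |
| 0.50 | 0.856 | 0.764 |
| 0.75 | 0.794 | 0.725 |

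With half the cohorts at odds ratio 2 and half at 4.5, mean power at 10 per cohort is 0.88: 0.97 in the stronger cohorts and 0.79 in the weaker ones.

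**The case against.** The strongest reply is that unequal effects are simulated and openly reported. Two and Half mix odds ratios of 1 and 3, their lower power is tabulated beside the Alternative column, and both documents say that power falls and type I error rises under such mixtures. That stands, so a reader who infers that the plan hides the cost of heterogeneity goes too far. It does not rescue the sentence, because neither scenario is a generally effective treatment, which is what the sentence describes.

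It may also be said that the absolute differences vary. They do, but only from 0.25 to 0.27, as a fixed odds ratio on unequal controls requires. The model borrows on the log-odds scale.

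A reader might infer that a common odds ratio of 3 is the best possible case for borrowing. Among the four simulated truths and the spreads tried here it gives the highest mean power, but it is not a strict maximum. One cohort at odds ratio 3 among cohorts at 4 had power of 0.926 against 0.919 at 10 per cohort, and 0.830 against 0.801 at 5.

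A reader might also blame lost borrowing for the low power of modest-effect cohorts. Small effects in about 10 patients are the main cause. Without borrowing (final look only, 0.80 cut), a cohort at odds ratio 2 has power of about 0.58; in the 2/4.5 mixture it has 0.79.

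Finally, nothing is miscalculated, all rates are printed, and no decision rule depends on the sentence. That is fair and limits the weight of the point.

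**Conclusion.** The point holds as a mismatch between the stated basis of the power and the scenario cited for it, and it appears in both documents. It rests only on the printed rates and the model's own effect scale. The tabulated 0.906–0.939 and 0.794–0.830 are power for a common odds ratio of about 3.

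The best measure of size is the plan's own: mean power for an effective cohort is 0.920, 0.835 or 0.772 at 10 per cohort, and 0.812, 0.666 or 0.583 at 5, depending on whether all, half or two of the cohorts respond. The graded-effect figures depend on assumed spreads and combine weaker effects with reduced borrowing, so they show direction and rough scale only.

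None of these figures should be read as this trial's actual power. Appendix R simulates eight example cohorts that omit glioblastoma and cholangiocarcinoma, and its final cut of 0.80 differs from the 0.90 in Protocol 10.4 and the SAP. That is a separate inconsistency; at 0.90 the common-odds-ratio case itself gives about 0.84 and 0.64.

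**What to change.** The simplest remedy is to correct the sentence in Protocol 10.8 and SAP 9. Remove the claim about varying effects, state that the quoted power assumes a common odds ratio of about 3 in all cohorts, and say that power is lower when effects differ, citing the Two and Half columns. This needs no new computation.

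The alternative is to keep the claim and make it true: add an all-effective scenario with graded odds ratios to Table 14-2 and SAP Table 2, label the chosen spread as an assumption, report power by effect size, and cite that column. This costs one more simulation scenario at each accrual rate. It would describe the generic framework unless the cohorts and final cut are also aligned with this trial.

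Neither option changes a stopping rule, minimum, cap or analysis. The downside is that the stated power looks somewhat less favourable.

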11.1 Regulatory and ethical compliance

This clinical study was designed, shall be implemented and reported in accordance with the International Conference on Harmonization (ICH) Harmonized Tripartite Guidelines for Good Clinical Practice (GCP), with applicable local regulations (including European Directive 2001/20/EC and US Code of Federal Regulations Title 21), and with the ethical principles laid down in the Declaration of Helsinki.

11.2 Responsibilities of the investigator and IRB/IEC/REB

The protocol and the proposed informed consent form must be reviewed and approved by a properly constituted Institutional Review Board/Independent Ethics Committee/Research Ethics Board (IRB/IEC/REB) before study start. A signed and dated statement that the protocol and informed consent have been approved by the IRB/IEC/REB must be given to Novartis before study initiation. Prior to study start, the investigator is required to sign a protocol signature page confirming his/her agreement to conduct the study in accordance with these documents and all of the instructions and procedures found in this protocol and to give access to all relevant data and records to Novartis monitors, auditors, Novartis Clinical Quality Assurance representatives, designated agents of Novartis, IRBs/IECs/REBs and regulatory authorities as required.

11.3 Informed consent procedures

Eligible patients may only be included in the study after providing written (witnessed, where required by law or regulation), IRB/IEC/REB-approved informed consent. Informed consent must be obtained before conducting any study-specific procedures (i.e. all of the procedures described in the protocol). The process of obtaining informed consent should be documented in the patient source documents. The date when a subject's Informed Consent was actually obtained will be captured in their eCRFs.

Novartis will provide investigators in a separate document with a proposed informed consent form (ICF) that is considered appropriate for this study and complies with the ICH and GCP guideline and regulatory requirements. Any changes to this ICF suggested by the investigator must be agreed to by Novartis before submission to the IRB/IEC/REB, and a copy of the approved version must be provided to the Novartis monitor after IRB/IEC approval.

Women of child bearing potential and fertile males should be informed that taking the study medication may involve unknown risks to the fetus if pregnancy were to occur during the study and agree that in order to participate in the study they must adhere to the contraception requirement for the duration of the study. Women of child bearing potential must agree to adhere to contraception requirement until at least 4 weeks after the final dose of study treatment. Fertile males must agree to adhere to contraception requirement until at least 12

weeks after the final dose of study treatment. If there is any question that the patient will not reliably comply, they should not be entered in the study.

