33. Known diagnosis of human immunodeficiency virus (HIV) infection (HIV testing is not mandatory).

34. Patient has a history of non-compliance to medical regimen

35. Pregnant or nursing (lactating) women, where pregnancy is defined as the state of a female after conception and until the termination of gestation, confirmed by a positive hCG laboratory test

[figure not shown]
36. Women of child-bearing potential, defined as all women physiologically capable of becoming pregnant, unless they are using highly effective methods of contraception during dosing and for 3 months following the discontinuation of study treatment.

Highly effective contraception methods include:

- Total abstinence (when this is in line with the preferred and usual lifestyle of the subject). Periodic abstinence (e.g., calendar, ovulation, symptothermal, post-ovulation methods) and withdrawal are not acceptable methods of contraception
- Female sterilization (have had surgical bilateral oophorectomy with or without hysterectomy) or tubal ligation at least six weeks before taking study treatment. In case of oophorectomy alone, only when the reproductive status of the woman has been confirmed by follow up hormone level assessment
- Male sterilization (at least 6 months prior to screening). For female patients on the study the vasectomized male partner should be the sole partner for that patient.
- Combination of the following (a+b or a+c, or b+c):
 - Use of oral, injected or implanted hormonal methods of contraception or other forms of hormonal contraception that have comparable efficacy (failure rate <1%), for example hormone vaginal ring or transdermal hormone contraception
 - Placement of an intrauterine device (IUD) or intrauterine system (IUS)
 - Barrier methods of contraception: Condom or Occlusive cap (diaphragm or cervical/vault caps) with spermicidal foam/gel/film/cream/vaginal suppository

In case of use of oral contraception women should have been stable on the same oral contraception for a minimum of 3 months before taking study treatment.

Oral contraceptives (OC), injected or implanted hormonal methods are not allowed as the sole method of contraception because BGJ398 has not been characterized with respect to the potential to interfere with PK and/or the effectiveness of OCs.

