7.1.4 Follow up period

7.1.4.1 Safety follow up

All patients who discontinue study treatment, including those who refuse to return for a final visit, will be contacted for safety evaluations (i.e., assessment of AEs and/or SAEs, concomitant medications) for 30 days after the last dose of study treatment. Patients whose treatment is interrupted or permanently discontinued due to an adverse event, including abnormal laboratory value, must be followed at least once a week for 4 weeks and subsequently at 4-weeks intervals until resolution or stabilization of the event, whichever comes first.

If patients refuse to return for safety evaluation visits or are unable to do so, every effort should be made to contact them by telephone to determine their status. Attempts to contact the patient should be documented in the source documents (e.g., dates of telephone calls, registered letters, etc.).

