7.2.2.6.6 Pregnancy and assessments of fertility

Women of childbearing potential must undergo a serum pregnancy test at screening to confirm eligibility in the trial (≤ 4 days before first dose of study drug), and at EOT. Women of child-bearing potential must additionally undergo a monthly urine pregnancy test during the treatment phase.

In case of pregnancy, the patient must permanently stop study treatment immediately, withdraw from the trial, and the pregnancy must be reported on the Clinical Trial Pregnancy Form.

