8.4 Pregnancies

To ensure patient safety, each pregnancy occurring while the patient is on study treatment must be reported to Novartis within 24 hours of learning of its occurrence. The pregnancy should be followed up to determine outcome, including spontaneous or voluntary termination,

details of the birth, and the presence or absence of any birth defects, congenital abnormalities, or maternal and/or newborn complications.

Pregnancy should be recorded on a Clinical Trial Pregnancy Form and reported by the investigator to the oncology Novartis Chief Medical Office and Patient Safety (CMO&PS) department. Pregnancy follow-up should be recorded on the same form and should include an assessment of the possible relationship to the Novartis study treatment of any pregnancy outcome. Any SAE experienced during pregnancy must be reported on the SAE Report Form.

Pregnancy outcomes should be collected for the female partners of any males who took study treatment in this study. Consent to report information regarding these pregnancy outcomes should be obtained from the mother.

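### Protocol 11.3 asks women to agree to only 4 weeks of contraception after the last dose, but exclusion criterion 36 requires 3 months: a gap of 61 to 64 days

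*Protocol*

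**What the plan says.** Exclusion criterion 36 in Protocol section 5.3 excludes women of child-bearing potential "unless they are using highly effective methods of contraception during dosing and for 3 months following the discontinuation of study treatment". Criterion 37 gives sexually active men the same 3 months after the last dose.

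Section 11.3 describes what patients must agree to at consent. It first states a general condition for women of child-bearing potential and fertile men: "in order to participate in the study they must adhere to the contraception requirement for the duration of the study". It then sets a specific period for women: "Women of child bearing potential must agree to adhere to contraception requirement until at least 4 weeks after the final dose". For fertile men the period is at least 12 weeks.

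Three other sections bear on the time after treatment:

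- Section 7.2.2.6.6 asks for a serum pregnancy test at screening and again at end of treatment, with monthly urine tests in between. Section 7.1.3.1 places the end-of-treatment visit within 14 days of permanent discontinuation.
- Section 7.1.4.1 says that patients who stop treatment "will be contacted for safety evaluations (i.e., assessment of AEs and/or SAEs, concomitant medications) for 30 days after the last dose of study treatment".
- Section 8.4 limits the reporting rule for patients' own pregnancies to the treatment period: "each pregnancy occurring while the patient is on study treatment must be reported to Novartis within 24 hours of learning of its occurrence".

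**The concern.** One safety rule has two stated minimum lengths, and the shorter one stands in the section that governs what a woman is asked to agree to. The 3 months lie in the future when she is screened, so her commitment is all that a site can confirm at that point. Section 11.3 also says that a patient whose compliance is in doubt should not be entered, which means the investigator must judge compliance against one period or the other. A woman who agrees to exactly the 11.3 minimum has not agreed to what criterion 36 requires.

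Little else is scheduled to cover the difference. The last planned pregnancy test is at end of treatment, and routine safety contact stops at day 30. Section 11.3 itself warns of unknown risks to a fetus. Amendment 3 re-opened enrolment, so this text applies to new consents.

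**Working it through.** **Start date.** Criterion 36 counts from discontinuation of study treatment and section 11.3 from the final dose. The glossary defines discontinuation as the point when the patient permanently stops BGJ398, so the two periods are taken to start on the same day.

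**Inputs.**

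- Criterion 36: 3 months. Counted from every start date in 2016 to 2020, three calendar months is 89 to 92 days.
- Section 11.3, women: 4 weeks = 4 × 7 = 28 days.
- Section 11.3, men: 12 weeks = 12 × 7 = 84 days.
- Section 7.1.4.1: safety contact for 30 days after the last dose.

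**Shortfall for women** = 3 months − 4 weeks: 89 − 28 = 61 days to 92 − 28 = 64 days.

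**Sensitivity to the meaning of 3 months.** Read as 90 days, the shortfall is 90 − 28 = 62 days. Read as 12 weeks, the most lenient reading, it is 84 − 28 = 56 days.

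**Part of the 3 months after routine safety contact** = 3 months − 30 days: 89 − 30 = 59 days to 92 − 30 = 62 days.

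**Men, for comparison** = 3 months − 12 weeks: 89 − 84 = 5 days to 92 − 84 = 8 days. The men's periods nearly agree, so only the women's figure departs materially from the eligibility rule.

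**Is there text that reconciles the two?** The condition in 11.3 that contraception be used for the duration of the study does not, because the sentence after it sets the specific post-dose minimum for women. No other section does either. Both conflicting sentences are current protocol text, not part of an amendment summary.

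**The case against.** The best reply is that the stricter rule already binds. Criterion 36 decides eligibility, section 7.1.1.2 allows no waivers, section 12 authorises no deviations, and section 9.2 requires full verification of the inclusion and exclusion criteria. A woman who would commit only to 4 weeks is therefore ineligible as the protocol stands, and since 11.3 sets a floor, 3 months meets both sections. This is correct, and it limits the practical risk to a site or consent form that takes its figure from 11.3. It does not remove the contradiction: 11.3 still states a required commitment that is too short for eligibility.

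Second, actual harm depends on the consent form, which was not available. That stands, and no claim is made about what women were told.

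Third, contact does not end completely at day 30. Patients who stopped because of an adverse event are followed until it resolves or stabilises (7.1.4.1), survival contact may continue every 3 months (7.1.4.3), and later SAEs, a category that includes congenital anomalies, are reportable if thought to be drug-related (8.2). Table 7-1 also times the safety visit from EOT. If that means a visit held 14 days after stopping, contact could fall as late as day 14 + 30 + 4 = 48, leaving 89 − 48 = 41 to 92 − 48 = 44 days. The 59 to 62 days follows the wording of 7.1.4.1 and depends on that reading. None of these contacts is a scheduled pregnancy test.

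Fourth, section 1.2.1.2.3 gives some pharmacokinetic data. Assuming linear once-daily kinetics, an accumulation ratio R implies a half-life of 24 h × ln 2 / ln[R/(R − 1)]. For R = 3 this is about 41 h. For R = 8 it is about 5.2 days, so 28 days is about 5.4 half-lives and roughly 2% would remain. This tempers the exposure concern. It does not cover the active metabolites, does not show that 4 weeks is safe, and is not offered in the protocol as a reason for a shorter period. If 4 weeks were intended, criterion 36 would be the text in error and the conflict would remain.

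**Conclusion.** The inconsistency is real. The 11.3 minimum for women is 61 to 64 days shorter than criterion 36 requires, or 56 days on the most lenient reading of 3 months. This rests on calendar months and on discontinuation and final dose being the same date, which the glossary supports. The number of women affected, the exposure remaining in the window and the wording of the consent form are all unknown. No estimate, error rate or analysis set is affected. It should be corrected because it is a patient-safety rule that, if followed as written in 11.3, falls short of the eligibility condition.

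**What to change.** In section 11.3, replace 4 weeks by 3 months for women of child-bearing potential, so that criterion 36 governs. Check that the consent form states 3 months for women, and inform enrolled women if it states the shorter period. While the paragraph is open, the men's 12 weeks could be changed to 3 months to remove the remaining 5 to 8 days.

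The cost is one phrase in the protocol and one check of the consent form. A notice to enrolled women is needed only if that check fails.
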